9.5. Responsibilities of the investigators

The investigators are responsible for:

- Grading the severity of AEs occurring from GA collection reported by study nurses as severe or potentially life-threatening
- Reporting SAEs, to the sponsor and to the appropriate country authorities.
- Assessing the causality of all SAE in relation to the study intervention and to concomitant intervention/medication.

The assessment on expectedness will be done by the sponsor.

SAEs, as defined above, should be reported as soon as they are known to the country CTU according to the last updated SOP. A specific "SAE report form" will be used. SAEs will be reported immediately by the country CTU to the INSERM Pharmacovigilance Department according to appropriate SOPs. If needed, queries on SAEs will be sent to the investigators by the INSERM Pharmacovigilance Department representative.

All SAEs must be reported if it they occur in a participant:

- from the date of signature of the informed consent to the study;
- during the follow-up of the participant scheduled by the study;
- until 4 weeks after the end of follow-up when it still could be related to the study intervention.

9.6. Responsibilities of the sponsor

9.6.1. SAE Recording and assessment

The sponsor shall keep detailed records of all SAEs which are reported to him by investigators.

The sponsor is responsible for the assessment of the causality of the SAE. In the absence of information on causality from the reporting investigator, the sponsor should consult the reporting investigator and encourage him to express an opinion on this aspect. The causality assessment given by the investigator should not be downgraded by the sponsor. If the sponsor disagrees with the investigator's causality assessment, the opinion of both the investigator and the sponsor should be provided in the report to the National Competent Authority.

All SAE for which the investigator or the sponsor considers that a causal relationship is a reasonable possibility are considered as suspected Serious Adverse Reaction (SAR).

The expectedness of the SAR shall be determined by the sponsor. The sponsor assesses if the SAE is expected or not using information described in the protocol (section 9.2), especially concerning, acts and methods performed for the research. An unexpected adverse reaction is an adverse reaction, the nature, the outcome or severity of which is not consistent with this information.

9.6.2. New fact reporting

When a new event is likely to affect the safety of participants, the sponsor and the investigator will take appropriate urgent safety measures to protect participants against any immediate hazard.

The sponsor will inform without delay the Competent Regulatory Authorities of safety data that may be relevant in terms of subject safety, or safety issues which might alter the current benefit-risk assessment of the study.

The INSERM Pharmacovigilance department shall transmit a written report to the Competent Regulatory Authorities and concerned Ethic Committees.

10. DATA COLLECTION AND PROCESSING

10.1. Description of data collected

10.1.1. Individual patient data

Once enrolled in the study, the following data will be collected for each patient by study nurses or will be extracted from databases of the TB-Speed SAM and HIV studies for children included in these two studies.

- Individual identifiers: month and year of birth, sex
- Co-enrolment in other studies
- Medical history
- Anthropometric and clinical data: weight, height, vital signs, symptoms, and AEs
- Radiological data: digital images and interpretation
- Dates of each specimen collection
- Laboratory data: HIV testing result, Ultra results, culture results

For each new patient included in the study, an anonymised individual identification code will be attributed and used as the only patient identifier in the REDCap database.

Radiological data will also be collected as digital imaging and communications files (.dicom files) and transferred to a FTPS in a server hosted at UBx. CXR interpretation will be directly reported in the patient's CRF using standardized forms developed as part of the capacity building component of the study.

Data transfer for dicom and gxx files is detailed in Chapter 10.3.6.

10.2. Definition of source data

Source data will be available to document the existence of patients enrolled in the study and should substantiate the integrity of the data collected. It will include the original documents relating to the study, the medical treatments and medical history of the patient.

The following information should be collected from source documents, where possible:

- Patient's demographic data (month and year of birth, sex)
- Details related to the study eligibility criteria
- Date of signing informed consent form
- Medical history and physical examination details
- Laboratory results

For the purpose of the study, specific forms may be developed for source data collection.

10.3. Electronic data entry

The eCRF system, the methods to ensure restricted access to the database, and the data management procedures, including the procedures to check completeness, accuracy, quality and validity of the data, will be described in specific study SOPs in accordance with good clinical, scientific and data management principles.

10.3.1. eCRF

Real time data collection is needed for optimised monitoring of data entry. No paper CRFs will be used; patient data collected at inclusion and follow-up visits will be recorded directly into an electronic CRF (eCRF) by study nurses, mostly through single data entry.

The TB-Speed data management system will be based on the electronic data capture application REDCap (Research Electronic Data Capture; https://www.project-redcap.org/). REDCap is an online tool for eCRF development, allowing data input from anywhere in the world over a secure connection with authentication and data logging.

Design and conception of the eCRF will be done by the international study manager in close collaboration with the international data manager and international clinical research assistant.

10.3.2. Data hosting

The REDCap MySQL database server will be hosted by the international CTU at the University of Bordeaux (UBx), France. REDCap is a free, secure web application for building and managing online surveys and databases, it's geared to support online and offline data capture.

Developed by Vanderbilt University, REDcap complies with internationally recognized standards including the Health Insurance Portability and Accountability Act (HIPAA, 1996), the United States legislation providing data privacy and security provisions for safeguarding medical information, as well as part 11 of Title 21 of the Code of Federal Regulations (CFR) that establishes the United States Food and Drug Administration (FDA) regulations on electronic records and electronic signatures.

10.3.3. Data security

The eCRF will be accessible 24 hours a day by secure authentication to a restricted users group. The connection will be authenticated by a user ID, password and digital certificate enabling data encryption during transfer and storage to the central server. Access levels will be granted and managed by the international data manager (international CTU).

[figure not shown]
The server hosted at UBx will be backed up every weekend on a hard drive, and send to bands (rotation frequency of the bands will be every five weeks). The database will be backed up incrementally on a hard drive every working day.

10.3.4. Data entry

Field-based users will be able to access REDCap either through a classical Internet-connected tablet or computer, or through the REDCap mobile App application.

The mobile App also enables offline data entry through a tablet or an Android mobile phone. In such a case, the tablet or mobile phone will be brought by the CRA to the country CTU and further synchronized with the central database once connected to the Internet (Figure 2).

Tablets will be purchased locally by country CTUs. Configuration of tablets will be managed by the international data manager.

Coptional data transfer in case main data transfer is unavailable

Figure 7. Secure data flow

Project Managers from country CTUs will be in charge of training relevant study staff for data collection and for issuing electronic data queries for quality control. The investigator is responsible for ensuring that all sections in the eCRF are completed correctly and that entries can be verified against source data. If the investigator authorizes other staff members to make entries into the eCRF, the names, positions, and signatures will be documented in writing. The eCRF will be completed during/after each study visit. Any person entering data in the eCRF will be trained beforehand and appointed to do this task.

10.3.5. Data coding

The Anatomical Therapeutic Chemical (ATC) system will be used for drug classification and coding. As part of safety monitoring, AEs will be coded using the Medical Dictionary for Drug Regulatory Affairs (MedDRA, version 17.1). Coding will be performed by country CTUs based at TB-Speed consortium members institutions.

10.3.6. Data transfer

Individual patient data will be transferred from tablets to the server located at UBx using a secure file transfer protocol (ftps) with individual authentication and data logging.

CXRs (dicom files) and Ultra test result files exported from GeneXpert (.gxx files) will be transferred to the international CTU central server using a secure web transfer (ftps). In case implementing sites experience web access issues, transfer of CXRs and Ultra result files will be done 1) by GSM with a tablet (equipped with a SIM card) from the implementing sites to the country CTU, and 2) from the country CTU to the international CTU central server via a secure web transfer (ftps). The study ID will be the only identifier in the electronic study database.

10.4. Description of the data verification, validation and processing (data management)

A data management SOP will be established and validated by the study coordination team at UBx. Verification of data completeness and consistency will be performed for all key data as well as a list of additional data defined in the DM SOP.

A data management system (DMS) will be developed at UBx within the REDCap database to enable generation of standardized lists of data management queries at country level. Queries will be programmed for data completeness, integrity and consistency. They will be run on at least a monthly basis at the country level. Data management checks will be implemented at the central level on a monthly basis. Furthermore, centralized correction queries will be sent by the international coordinating CTU to the country CTU. The investigator, co-investigators, head of laboratory must allow access to relevant hospital, laboratory or clinical records, to confirm their consistency with the CRF entries. All research staff working in the study, including study nurses, national CTU team (PMs, CRAs), PIs, international coordination team (CRA, Trial Manager, Coordinating

Investigators) will sign a confidentiality agreement with regards to access to individual patient data and medical records.

Central statistical monitoring will also be implemented by the international coordinating CTU to look at variables for which distributions differ from the rest of the observed data at the country, site or patient level. Its purpose is to highlight systematic (non-random) faults in data collection and study implementation procedures and to guide targeted monitoring. Variables subject to statistical monitoring are specified in the monitoring plan. Comparison of distributions is made by statistical tests or models.

Before database freezing, a final data review will be conducted by the international data manager and remaining issues will be adjudicated.

10.5. Length of data retention, archiving conditions and management

In addition to the source medical records, radiological data will be collected as digital imaging and communications files (.dicom files). CXR interpretation will be directly reported in the patient's CRF using standardized forms developed as part of the capacity building component of the TB-Speed study.

In the same way, Ultra test result files (.gxx files) will be extracted directly from the GeneXpert software and mycobacterial source data will be obtained from the laboratories registers and logs.

Data transfer for dicom and gxx files is detailed in Chapter 10.3.6.

All data will be stored in a server hosted by the CREDIM (*Centre de Recherche et Développement en Informatique Médicale*) at UBx.

The server is located in a secure computer room. The network is protected by uninterrupted power supply firewalls and up-to-date virus and malware scanning software. Data backups are performed regularly. Reading, entry, modification or deletion of data will be granted via the standard authentication and access-control features.

Medical records will be stored in the clinical sites as per standard practices. Electronic data and files will be maintained on password-protected computers. Essential study documents will be retained at the coordinating centre for 15 years.

No displacement or destruction of data will be done without the agreement of the sponsor. At the end of the regulatory archiving period, the sponsor will be consulted for destruction.

10.6. Study documents archiving conditions and management

Essential documents and study records will be kept secured of a minimum of 15 years after study completion, under the responsibility of each country investigator, the international CTU, and the sponsor.

Study documents will be made available online to investigators on a secured website. The international coordinating CTU will be responsible for routinely updating global documentation on the study website. Country CTUs will be responsible for routinely updating national documentation on the study website.

Investigators will ensure that study records are not disposed of or removed from the study sites or the country CTU without prior notification and approval from the sponsor or his representative.

Each investigator will keep a hard copy of original documents whenever those are manually signed or generated. This includes, at site level, medical records (source documents) and study ID assignment log which are subjected to professional secrecy and confidentiality, and task delegation lists.

Data, documents, reports and SOPs should be available to be audited or inspected at any time.

11. STATISTICAL DATA ANALYSIS

11.1. Statistical analysis manager

The statistical analysis manager will be the study statistician, based at UBx.

The statistical analysis plan will be written by the study statistician and validated by the coordinating investigators.

11.2. Description of the statistical analysis plan

11.2.1. Analysis of the primary endpoint

Sensitivity of the 4 Ultra on stool using TB culture reference standard (LJ and MGIT) in respiratory sample: point estimate and 95% CIs.

Specificity of the 4 Ultra on stool using TB culture reference standard (LJ and MGIT) in respiratory sample: point estimate and 95% CIs.

We will use as TB culture reference standard:

- Positive: at least one positive MTB culture result in one of the two respiratory samples
- Negative: negative culture results from 2 samples without any positive result

An intention-to-diagnose analysis will be performed at:

- Sample level (denominator: total number of samples collected): 1 stool vs the TB culture reference standard
- Patient level (denominator total number of cases with at least one stool sample collected): at least 1 of the two stools vs the TB culture reference standard.

A patient will be classified as stool positive, when they have at least one positive stool Ultra result (for example the first stool may not have any positive Ultra results, but the second stool could have 1 positive Ultra result, in which case the patient would be considered stool positive).

Invalid Ultra results, contaminated and NTM culture results will be considered negative.

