4. STUDY DESIGN

4.1. Study type

This is a diagnostic study evaluating the diagnostic accuracy of the Ultra assay in stools with a two-stage sequential design starting as a cohort of children with presumptive TB enriched in a second stage with Ultra positive TB cases on respiratory sample. It is both an ancillary to the TB-Speed HIV and the TB-Speed SAM studies and a study enrolling children from routine not enrolled in those two studies.

This design was chosen to be able to evaluate the sensitivity and specificity of the Ultra assay in a smaller sample size that is usually required by a "classical" prospective cohort design and avoiding the bias of overestimation of the sensitivity classically associated with the case-control design. In order to quickly generate data on appropriate stool processing method, and to contribute to the planned WHO recommendations for stool Ultra testing (expected 2nd semester 2021), we will use a two-stage sequential design. Indeed, knowing that on average only 10-15% of children with presumptive TB in a community-based setting will be confirmed, in order to reach the sample size of confirmed cases for the evaluation of sensitivity, 7 to 10 times more children with presumptive TB would need to be enrolled in a prospective design. On the other hand, the number of children with presumptive TB not confirmed with TB for the estimation of the specificity would be reached much earlier. In addition, based on the previous study results, we know that the specificity of Xpert MTB/RIF assay in stool is high (99% CI:98-99; [32]), which would result in a relatively small sample size to evaluate the specificity of the Ultra in stools.

During the first stage, we will offer to join all consecutive presumptive TB cases presenting at study sites to estimate specificity with the expected precision and calculate a preliminary sensitivity estimate. During the second stage, we will keep enrolling only those from TB Speed studies and routine care who are Xpert positive on respiratory samples in order to estimate sensitivity with the expected precision.

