This two-stage sequential design first estimating specificity then sensitivity has been described by Wruck *et al.* [43] as an efficient way of validating diagnostic tests when the prevalence of the disease is low. It would not be feasible to consecutively enrol all children with presumptive TB to describe an expected sensitivity of 60% with 10% precision as this would require over 900 patients, of which, approximately 800 would be culture negative. In the two-stage process described by Wruck, only reference standard positive samples from the original population are selected in stage 2. We adapted this design to the TB context as culture results will only be available after enrolment (and if the child is positive, only after they have started treatment), hence selecting only those who are Ultra positive on respiratory samples for the second cohort as a way of enriching the study population with a subpopulation that has a higher TB prevalence probability, before their true disease status

is confirmed. Other comparable diagnostic studies have either used greater resources to include larger samples sizes (Dorman [14] and Wang [44]) or have resorted to reporting imprecise estimates of sensitivity [79-84]. To our knowledge, this is a relatively unique approach to study design for accuracy studies, with few published examples [45,46].

With such design, there should be no bias on the evaluation of the specificity similarly to a classical prospective design because this evaluation will be done among consecutively enrolled children with presumptive TB only. The sensitivity estimates may not be generalizable to all culture confirmed TB children due to the sampling approach. Xpert positive children will be more likely to have higher biological loads, causing a possible inflation of the sensitivity. However, the results will provide valuable information on variations of sensitivities of the different stool processing methods within this population.

We will carry out an interim analysis after the completion of the prospective cohort in order to describe specificity and preliminary results of the sensitivity and the agreement between the processing methods. The recruitment of participants will not be put on hold during the interim analysis. We will conduct a final analysis at the end of the study to describe sensitivity as well as the secondary end points.

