4.3. Sample size

As we want to estimate two proportions, specificity and sensitivity, we need to ensure a sufficient sample size for these two estimates.

The first stage is to estimate specificity by enrolling children with presumptive TB. With an expected specificity of Ultra in stool of 90%, the minimum sample size to estimate specificity with 5% precision, is 140 children with presumptive TB and negative TB culture from two respiratory samples. Inflating this number by 15% for attrition (to a total of 160 children) and considering a 10% prevalence of culture-confirmed TB in our population, we will need to enrol a total of 177 children with presumptive TB.

The second stage is to estimate sensitivity among presumptive TB children with culture confirmed TB. With an expected sensitivity of Ultra in stool of 60%, based on a literature review, the minimum sample size to estimate sensitivity with 10% precision, is 93 children with culture-confirmed TB. Inflating this number by 10% for attrition and invalid results, we will need a total of 103 confirmed TB cases. We expect 16 culture confirmed to be enrolled during the first stage (10% of 160 children enrolled in the prospective cohort). Then we will need to enrol an additional 87 children during the 2nd stage from presumptive TB children with a respiratory sample positive with Xpert Ultra (enrichment cohort). Knowing that only 90% of these children will ultimately be culture positive, we will need to further inflate the number of children to be recruited based on Ultra result in their respiratory sample [84]. We will therefore a total of enrol 97 children with Xpert Ultra positive results during the second stage.

Given routine site data and estimated enrolment figures for the Ugandan and Zambian study site, we expect to enrol children for the first stage in approximately 12 months, and Ultra-positive children for the second stage in 11 months.

For the secondary endpoints, in order to test Kappa coefficients with a minimum acceptable value of 0.4 [47], considering the study sample size, we will be able to detect a minimum change of 0.1 in Kappa coefficient between the stool sample processing methods with 80% power.

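### As the protocol states it, the primary sensitivity combines unselected cases with cases enrolled for a positive respiratory Xpert, so it is likely biased upward for children with presumptive TB, and section 11 makes no adjustment

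*Protocol*

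**What the plan says.** The primary objective (section 2.1) is diagnostic accuracy of stool Ultra in children with presumptive TB. Section 11.2.1 gives the estimator: "Sensitivity of the 4 Ultra on stool using TB culture reference standard (LJ and MGIT) in respiratory sample: point estimate and 95% CIs". Appendix 1 repeats it. Neither place mentions cohort, respiratory Xpert status or weighting.

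Section 4.3 sizes this estimate with one proportion. It starts from "With an expected sensitivity of Ultra in stool of 60%, based on a literature review" and states that "the minimum sample size to estimate sensitivity with 10% precision, is 93 children with culture-confirmed TB". It continues: "Inflating this number by 10% for attrition and invalid results, we will need a total of 103 confirmed TB cases". Sixteen of these are expected from stage 1. For the remainder, "Then we will need to enrol an additional 87 children during the 2nd stage from presumptive TB children with a respiratory sample positive" on Xpert Ultra. The protocol does not use the word pooled; that one denominator combines both stages is inferred from sections 4.3 and 11.2.1 read together.

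Section 4.1 makes two statements about bias. It presents the design as "avoiding the bias of overestimation of the sensitivity classically associated with the case-control design". It later says that the sensitivity may not generalise to all culture-confirmed children and that "Xpert positive children will be more likely to have higher biological loads, causing a possible inflation of the sensitivity". It adds that the results remain informative on differences between methods within this population.

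**The concern.** Stage 2 selects children on a positive result from the same assay family as the index test. Respiratory and stool results both depend on bacterial load, so these children are more likely to be stool-positive than culture-confirmed children in general. Section 4.1 notes that the cited two-stage design selects reference-standard positives in its second stage. The protocol replaces that with respiratory Xpert positives because culture results arrive too late. This substitution changes what the combined proportion estimates: it moves close to sensitivity given culture-positive and respiratory Xpert-positive status, while the objective still names children with presumptive TB.

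The absolute sensitivities of four methods are the primary result and are meant to inform WHO recommendations. An unlabelled combined figure would be read as the yield to expect in all culture-confirmed children, including those whom respiratory Xpert misses.

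**Working it through.** **Reproducing the plan (section 4.3).**
- 1.96² × 0.60 × 0.40 / 0.10² = 92.2, so 93.
- 93 × 1.10 = 102.3, so 103.
- 103 − 16 = 87; 87 / 0.90 = 96.7, so 97 enrolled in stage 2.

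All stated figures reproduce.

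**Inputs for the check.**
- r, the share of culture-positive children who are respiratory Ultra-positive: 64.5% and 75.3% on one sample, and 71% on frozen samples (section 1). Because the study tests two samples, 85% is added as an assumption.
- s0, stool sensitivity in culture-positive, respiratory Xpert-negative children: not in the protocol. Assumed 20-40%.
- True sensitivity in all culture-positive children: 60%, the planning value.

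**Make-up of the denominator.** Xpert-positive share = (16r + 87)/103. At r = 64.5% this is 97.3/103 = 94.5%; at r = 75.3% it is 99.0/103 = 96.2%.

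**Bias.** Solve 0.60 = r·s1 + (1 − r)·s0 for s1, the stool sensitivity in Xpert-positive cases. Then combined = (16 × 0.60 + 87 × s1)/103.

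Example with r = 71%, s0 = 30%: s1 = (0.60 − 0.29 × 0.30)/0.71 = 0.7225; combined = (9.6 + 62.86)/103 = 70.4%; bias +10.4 points.

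| r | s0 | s1 | combined | bias (points) |
|---|---|---|---|---|
| 64.5% | 20% | 82.0% | 78.6% | +18.6 |
| 64.5% | 40% | 71.0% | 69.3% | +9.3 |
| 71% | 20% | 76.3% | 73.8% | +13.8 |
| 71% | 40% | 68.2% | 66.9% | +6.9 |
| 75.3% | 20% | 73.1% | 71.1% | +11.1 |
| 75.3% | 40% | 66.6% | 65.5% | +5.5 |
| 85% (assumed) | 20% | 67.1% | 66.0% | +6.0 |
| 85% (assumed) | 40% | 63.5% | 63.0% | +3.0 |

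The bias is zero if s0 = s1. Read the other way, a combined result of 60% would imply a target-population sensitivity of 47.3% to 55.7% for r = 64.5-75.3% and s0 = 20-40%.

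**What stage 1 can correct.** Section 4.2 has respiratory Ultra, culture and stool Ultra on every stage-1 child, so r and s0 can be estimated there. The weighted estimate r·s1 + (1 − r)·s0 has variance r(1 − r)(s1 − s0)²/n1 + r²s1(1 − s1)/n₊ + (1 − r)²s0(1 − s0)/n₋. Here n1 = 16, n₊ = 16r + 87 and n₋ = 16(1 − r), each multiplied by 93/103 for attrition.
- At r = 71%, s0 = 30%: 0.00254 + 0.00114 + 0.00422 = 0.00790, half-width 1.96 × √0.00790 = ±17.4 points.
- Across the table: ±13.6 to ±20.3 points.
- Stage 1 alone: 1.96 × √(0.24/16) = ±24 points.
- Expected culture-positive, Xpert-negative children in stage 1, before attrition: 16 × 0.355 = 5.7 down to 16 × 0.15 = 2.4. At r = 85% the chance of none is 0.85¹⁶ = 7%.

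**Precision of the conditional estimate.** With r = 64.5-75.3%, n₊ after attrition is about 88 to 89. At 60% the half-width is 1.96 × √(0.24/88) = ±10.2 points, so the planned size nearly delivers the stated precision for Xpert-positive children.

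**The case against.** The protocol does not hide the problem. Section 4.1 warns of inflation, limits generalisability and points to comparison between methods as what the data can support. Those comparisons are made within child by McNemar tests (section 11.2.2), so this point does not touch them. The interim analysis (sections 4.1 and 11.2.3) already yields a preliminary stage-1 sensitivity free of enrichment. A separate statistical analysis plan is foreseen in section 11.1 and could add stratification or weighting. All of this stands. It does not settle the matter, because the primary endpoint is absolute sensitivity, and sections 4.3 and 11.2.1 fix its denominator, precision and form without carrying the caveat over.

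Four stronger readings are tempting but not supported:
- That the bias equals the 10-point precision. This needs s0, which the protocol does not give, and the cited r values rest on one sample while the study tests two.
- That the confidence interval is falsely narrow. It is right for the mix of children sampled; the mismatch is with the target population.
- That section 4.1 claims freedom from bias. The statement compares the design with case-control studies; it is in tension with the later concession, not a flat denial of it.
- That a weighted estimate would be unbiased and should become primary. Stage 2 admits MTB/RIF or Ultra on one sample, including NPA (sections 4.2 and 5.1.2), and routine wards do not sample systematically (section 7.1.2). Stage 1 uses Ultra on two sputum or gastric aspirate samples. Xpert-positives from the two stages may therefore differ, and the Xpert-negative term rests on about 2 to 6 children.

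**Conclusion.** The concern holds for what the protocol states. The planned sensitivity mixes two selection rules in one denominator, about 94-96% of it respiratory Xpert-positive, and is biased upward for children with presumptive TB whenever stool detection is lower in Xpert-negative cases. Section 4.1 itself gives the reason to expect this. The direction is well supported; the size is not fixed by the documents. With true sensitivity at 60% and s0 assumed at 20-40%, the bias is about +5.5 to +18.6 points at the cited one-sample respiratory sensitivities and about +3 to +6 points at an assumed 85%. The ±10 precision can be claimed, approximately, only for the conditional estimate in respiratory Xpert-positive children.

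**What to change.** In section 11.2.1, with matching edits to sections 4.1 and 4.3 and Appendix 1:

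1. Report, for each method, sensitivity among culture-confirmed, respiratory Xpert-positive children from both stages, labelled as conditional on that status. Attach the 10% precision in section 4.3 to this estimate only.
2. Report stage-1 sensitivity separately in the final analysis as the unselected estimate. Do not present the combined figure as sensitivity in children with presumptive TB.
3. Add as a supporting analysis w·Se(Xpert+) + (1 − w)·Se(Xpert−), with w and the second term from stage 1, the first term from both stages, and an interval that carries the uncertainty in all three (for example a bootstrap by child within stage). State the assumption that stage-1 and stage-2 Xpert-positives are exchangeable, that the second term rests on about 2 to 6 children, and what will be reported if there are none.
4. Reconcile the two statements on overestimation in section 4.1.

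This changes wording and analysis only and uses data already collected. The cost is that sensitivity for the target population will carry a half-width of about ±14 to ±20 points when weighted, or about ±24 from stage 1 alone, both wider than the stated ±10.
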